### **11b Criteria for discontinuing or modifying allocated interventions**

Exercise sessions begin with assessing the progression of the tendon healing. In the first weeks with immobilization and physical examination is not possible, the participant is asked if there has been any constant or sudden pain or swelling and if there has been any excessive load to the tendon. At the 2-week appointment in the outpatient clinic the standard procedure is to examine any reported symptoms and perform a physical examination of the tendon and muscle structure.

In case of deviation from the protocol or adverse events, the Data and Safety Monitoring Board (see 21.a) will decide to either continue with modifications or to withdraw the participant from the study.

### **11c Strategies to improve adherence**

During the first visits, the participants are informed about the importance of adherence to the exercise intervention. At the sessions the physiotherapists will use verbal encouragement to motivate the patients to perform the exercises. To promote adherence to the home exercise program there will be a pamphlet with detailed description of the exercises and a training journal.

Each appointment will be registered in the hospital booking system and this features a possibility of having text messages prior to the appointments. If the participant fails to attend an appointment, the physiotherapist will arrange another appointment. If the participant decides to leave the study, the reason for leaving will be registered.

### **11d Relevant concomitant care and interventions that are permitted or prohibited**

During the first nine weeks of treatment the patients are advised to avoid activities with high load on the foot, and to focus on oedema prophylaxis and training for a better overall result. Most activities of daily living will be possible, but it is advisable to take sick leave from work in the first two to nine weeks or longer depending on the workload.

## **12. Outcomes**

During the initial clinical examination, we will collect the following descriptive data: age, height, body mass, educational level, work and sports activity status, trauma cause and smoking.

### **Primary outcome:**

The primary outcome is Achilles tendon Total Rupture Score (ATRS), which is a validated self-reported questionnaire for acute Achilles tendon rupture.(28) It consists of 10 items concerning

limitations related to symptoms and physical function. Each item is rated from 0 (very limited function) to 10 (not at all limited). Items: strength, fatigue, stiffness, pain, activities of daily living, walking on uneven surfaces, walking quickly upstairs or uphill, running, jumping and hard physical labour. The ATRS is validated in a Danish population and is used in the Danish Achilles Database DADB.(12,34) The primary endpoint is 13 weeks. The questionnaire will also be filled out at baseline to re-call a pre-rupture level and at the 26- and 52-weeks follow-up.

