## 10. Eligibility criteria

Inclusion criteria:

- Patients with acute total Achilles tendon rupture treated non-surgically (Standard care of treatment in North Denmark Region)
- Diagnosed within 3 days (of their injury)
- Age 18 - 65, able and willing to participate in the intervention
- Able to speak and understand Danish

Exclusion criteria:

- Achilles tendon rupture close to insertion on calcaneus or in the musculo-tendinous junction of the triceps surae
- Previous Achilles tendon rupture or other conditions in either leg causing lower leg disability (pain, deficits in strength or range of movement)
- Treated with Fluorquinolons or Corticosteroids within the last 6 months
- Diabetes or rheumatic diseases
- Severe medical illness: ASA score higher than or equal to 3.(33)

Excluded patients and patients not willing to participate will follow the usual program of rehabilitation for non-surgical treatment at the hospitals.

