The Tampa scale of Kinesiophobia (TSK) is used and validated for backpain, but has previously been used for Achilles tendon rupture evaluation as the questions about kinesiophobia could have associations to how patients with Achilles tendon rupture manage rehabilitation and return to sports.(40) The questionnaire consists of 17 items concerning pain and kinesiophobia and has 4 answers from “Strongly disagree” to “Strongly agree”. Measured at baseline, 9, 13 and 52 weeks.

Question: Were you afraid to do the prescribed load when performing the exercises? If yes why?  
Measured at 9 weeks

**Compliance with the intervention:** The participants will register the number of exercise sessions they perform each day in a training journal. The timeframe will be from the day they start the exercises to the end of week 9.

**Safety and Adverse events.** The number of serious and minor adverse events is registered in a pre-defined list based on Common Terminology Criteria for Adverse Events(43) and the participants will be asked open questions at each session. Serious adverse events are re-rupture, non-union of the tendon or symptomatic deep vein thrombosis (DVT). Muscle soreness or mild pain is considered inevitable and normal when initiating exercises after a period of immobilization.

**Cost-effectiveness outcomes.** To evaluate the cost-effectiveness of the intervention, we will use self-reported health state as measured by the EQ-5D-5L.(44) Work productivity outcomes are measured using the Work Productivity and Activity Impairment Questionnaire WPAI:GH and condition-related expenses as measured by a self-developed questionnaire. The EQ-5D provides a simple descriptive profile and a single index value for health status and has been used extensively in research to measure QALYs gained and thereby perform health economic evaluations. The questionnaires will be filled out during all follow-ups.

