## 14. Sample size

Sample size calculations are based on the primary endpoint ATRS with a clinically relevant difference at 10 point and estimated standard deviation 15 point. With a two-sided 5% significance level and a power of 80%, the sample size will be 37 in each group and a total of 82 participants when allowing for potential dropouts.

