### 3.2. Randomization and Blinding

The randomization procedure:

The participants will be allocated to two groups in a 1:1 randomization using a computer-generated sequence on [www.sealedenvelope.com](http://www.sealedenvelope.com). A staff member with no connection to the project will be responsible for generation of the randomization key and numbered sealed opaque envelopes.

The randomization will be Permuted Block Randomization in block sizes of 2, 4 and 6 with stratification for hospital allocation to allow for minor differences in the treatment (the intervention will be the exact same at the two places, but there could be minor differences in treatment procedure) due to different logistic/culture at the two hospitals. As there is a male to female ratio of 3-5:1 sex is also added to the stratification.

Blinding procedure:

The participants and the physiotherapist supervising the exercise sessions cannot be blinded. The physiotherapist performing the outcome assessment at follow-up will be blinded to the group allocation. The assessor will not be involved in the intervention or be affiliated with the treatment sites. Participants are asked to keep the group allocation secret from assessor. The principal investigator and the statistician performing the statistical analysis will be blinded.

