### ***6.1. Primary Endpoint***

Descriptive statistics (mean (standard deviation) or median (interquartile range) for continuous variable or frequencies and proportions for categorical variables) will be used to describe demographics, for the two treatment groups individually and overall sample.

The primary intention-to-treat analysis will investigate the between-group difference in ATRS. We will use a linear mixed effects regression model with the participant as random effect and time 13, 26 and 52 weeks, group allocation (standard care vs standard care plus add-on) and baseline value as fixed effects. Conclusions will only be drawn based on the primary endpoint (13 weeks). We will use Q-Q plots and histograms to assess data normality.

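### The primary model's only baseline covariate is a recalled pre-rupture ATRS that probably sits near the top of its scale, so a modest, cheap gain in precision is likely being missed

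*Protocol*

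**What the plan says.** Protocol 20a and SAP 6.1 specify the same primary model: a participant random effect, time (13, 26 and 52 weeks), and "group allocation (standard care vs standard care plus add-on) and baseline value as fixed effects". No other covariate is listed, and Protocol 20b has no adjusted analyses.

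The baseline ATRS is not a post-injury measurement. Protocol section 12 states: "The questionnaire will also be filled out at baseline to re-call a pre-rupture level". The participant timeline calls it a pre-score, and SAP 2.3 lists it under pre-injury status.

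Protocol section 10 excludes "Previous Achilles tendon rupture or other conditions in either leg causing lower leg disability (pain, deficits in strength or range of movement"). SAP section 4 has the same exclusion. The ATRS items cover strength, stiffness, pain, walking, running and jumping, and the top of each item means no limitation.

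Other baseline data are collected but not modelled. Age is among the descriptive data in Protocol section 12 and SAP 2.3. The TSK is "Measured at baseline, 9, 13 and 52 weeks". Sex is a stratification factor in both documents, and Protocol 16a gives a lower ATRS outcome in women as part of the reason. Protocol 16c has the baseline questionnaires completed before the envelope is opened.

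**The concern.** Baseline adjustment improves a randomised comparison to the extent that the covariate predicts the outcome. Here the eligibility rule removes people whose legs were limited before the rupture, and the covariate asks how limited the leg was before the rupture. A score compressed against its ceiling usually correlates less with later outcome than an unrestricted one. It also says nothing about the patient's state after injury.

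The model may therefore look baseline-adjusted while having close to the precision of an unadjusted comparison. Meanwhile sex, the one baseline variable that the protocol itself links to the ATRS, is left out. What is at stake is the width of the confidence interval for the single 13-week contrast on which all conclusions rest, in a trial of 82 patients.

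**Working it through.** **Inputs from the documents.** Protocol section 14 gives a "clinically relevant difference at 10 point and estimated standard deviation 15 point", two-sided 5% significance and 80% power, and concludes that "the sample size will be 37 in each group and a total of 82 participants when allowing for potential dropouts". Allocation is 1:1 (SAP 3.2). The male-to-female ratio of 3–5:1 (Protocol 6a) means 17–25% women.

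**Inputs that must be assumed.** The documents give no mean, SD or ceiling share for the recalled score, and no correlation of any baseline variable with the 13-week ATRS. Every R² below is an assumption.

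**1. The plan's own figure.** The standard error is 15 × √(2/37) = 3.487 and the noncentrality is 10/3.487 = 2.867, on 72 degrees of freedom. The t-test power is 80.8% with 37 per group and 79.7% with 36, so 37 is reproduced. The 95% half-width is 1.993 × 3.487 = 6.95 points. The raw SD of 15 is used, so no credit is taken for adjustment.

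**2. What a ceiling does.** A normal latent baseline was simulated and capped at the top score. The table shows the R² that remains.

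| Latent r | No cap | 50% at top | 75% at top | 90% at top |
|---|---|---|---|---|
| 0.2 | 4.0% | 2.9% | 2.0% | 1.1% |
| 0.3 | 9.0% | 6.6% | 4.4% | 2.4% |
| 0.5 | 25% | 18% | 12% | 7% |

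A ceiling weakens the covariate without making it useless.

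**3. What sex could explain.** With proportion p of women and an assumed sex difference d, R² = p(1 − p)d²/15². For d = 10 this is 0.25 × 0.75 × 100/225 = 8.3%, or 6.2% with p = 1/6. For d = 5 it is about 2%, and for d = 15 it is 14–19%.

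**4. Power now and after the change.** The noncentrality is 10/[15 × √(1 − R²) × √V × √(2/37)]. V = 71/(71 − k) is the expected variance inflation from chance imbalance in k covariates among 74 patients. Now: k = 1, V = 71/70 = 1.014, 71 degrees of freedom. After adding sex, age and TSK: 68 degrees of freedom, with k = 3 because stratification roughly balances sex, so V = 71/68 = 1.044. R² is the total explained by all covariates in the model.

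| Total R² | Recalled ATRS alone | With sex, age, TSK | With sex, age, TSK, V ignored |
|---|---|---|---|
| 0% | 80.2% | 79.0% | 80.7% |
| 4% | 81.8% | 80.6% | 82.3% |
| 10% | – | 83.0% | 84.6% |
| 15% | – | 85.1% | 86.6% |
| 20% | – | 87.1% | 88.5% |

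Ignoring V, the half-width is 6.60, 6.41 and 6.22 points at R² of 10%, 15% and 20%.

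**5. Break-even.** The change raises V by a factor of 70/68 = 1.029, so the added covariates must explain about 3% of the variance to pay for themselves. If they explain nothing, power goes from 80.2% to 79.0%. If stratification failed to balance sex (k = 4), these become about 4% and 78.4%.

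All of this is a two-sample approximation at 13 weeks. The planned mixed model over three visits would have a different precision, which depends on within-patient correlations that are not given.

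**The case against.** The strongest reply is that this is an efficiency preference resting on undocumented assumptions. Much of it stands.

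- A reader might infer that the recalled score is nearly constant and that the adjustment achieves almost nothing. The documents do not show that. The exclusion concerns conditions causing lower leg disability. The ATRS also asks about fatigue, running, jumping and hard physical labour in adults up to 65, so some spread is likely. With 75% at the top and a latent correlation of 0.5, R² is still 12%.
- A reader might infer that the trial is underpowered or biased. It is neither on this account. The sample size used the unadjusted SD, and power remains about 80% even if the covariate explains nothing. The recall is completed before allocation is known.
- A reader might infer that age and TSK are established predictors. The protocol gives age no link to outcome. It says only that fear might affect loading and that kinesiophobia might relate to how patients manage rehabilitation. Sex is the only variable that it ties to the ATRS.
- Assigning a low R² to recalled ATRS and a higher one to a fuller set builds the gain into the assumptions. The power figures are therefore an illustration and not evidence of a gain.

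The objection does not remove the structural point. The sole covariate is restricted by design, the one variable that the protocol links to the ATRS is left out, and the remedy uses data already collected.

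**Conclusion.** The point holds as a likely missed gain in precision. That the only baseline covariate is a recalled pre-rupture ATRS is documented. That it clusters near the top is a reasonable inference from the eligibility rules, and that it removes little variance is likely but not established. Under assumed R², and on the 13-week approximation, power is about 80–82% now (recalled score explaining 0–4%) and about 83–88% if the fuller set explains 10–20% in total. The lower end of that range allows for chance imbalance and the upper end largely does not. The planned 80% power and the validity of the comparison are not in question. The change is worth making because it is cheap and its downside is small and known.

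**What to change.** In SAP 6.1 and Protocol 20a, before unblinding:

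- State that the baseline value is the recalled pre-rupture ATRS, and keep it in the model.
- Add sex, age (continuous) and baseline TSK total (continuous) as prespecified fixed effects.
- Replace missing baseline values by the overall mean across both arms, so that no randomised patient is dropped.
- Report the model with recalled ATRS alone as a sensitivity analysis.

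Protocol 16a stratifies by sex only and SAP 3.2 by hospital and sex. Reconcile them, so that it is clear whether hospital is also a stratification factor to consider for the model.

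The cost is a few sentences, three degrees of freedom and no new data. If the added covariates explain less than about 3% of the variance there is no gain, and the loss is at most about one point of power. The set must be fixed before unblinding, because covariates chosen afterwards would not be credible.

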**Secondary outcomes:**

**International Physical Activity Questionnaire (IPAQ)** short form Danish version. It consists of 7 items concerning physical activity as time spent performing vigorous and moderate activities, the time spent walking and sitting during the past week. The IPAQ gives an estimate of the total weekly physical activity measured in MET-minutes per week and total minutes spent sitting.(35) The questionnaire will be filled out at baseline (to re-call a pre-rupture level) and at the 13, 26 and 52 weeks follow-up.

**Achilles tendon resting angle (ATRA)** is validated as an indirect measure of the Achilles tendon length.(36–38) The ATRA will be measured at 13 and 52 weeks.

**Ability to perform a standing Heel-rise.** The participants will be classified as being able to perform a single-leg heel-rise if they are able to lift the heel at least 2 cm while keeping the knee straight. Position is standing with ankle in a neutral position and fingertips on the wall for balance support.(39,40) Measured at 13 and 52 weeks.

**Achilles tendon properties - length** measured by ultrasound using Copenhagen Achilles length measure (CALM) for tendon length(41) will be performed at 9, 13 weeks and 52 weeks.

**Isometric muscle strength** – is measured as maximal isometric plantar flexor muscle strength using a Fysiometer.(42) The leg is placed on a Wii platform and secured with a belt around the knee and the Wii platform. When the isometric contraction is performed, the Wii is calculating the maximum peak force and the rate of force. Position: seated with 90 degrees flexion in hip and knee. Measured at 9, 13, 52 weeks.

**Muscle endurance** is measured with the MuscleLab measurement system (Ergotest Technology, Oslo, Norway).(39) External weight load on the knee is calculated to 50% of the bodyweight. A linear encoder is attached to the heel of the shoe. When heel-rise is performed, the string is pulled, and the sensor measures the muscle endurance. Measured seated at 13 weeks and standing at 52 weeks.

**The fear of re-rupture.** When asked, patients often mention the fear of re-rupture and feeling the “pop” of the tendon as the worst thing that could happen again. This could influence the willingness to participate in the early exercises and how much they will load during the exercises.

The Tampa scale of Kinesiophobia (TSK) is used and validated for backpain, but has previously been used for Achilles tendon rupture evaluation as the questions about kinesiophobia could have associations to how patients with Achilles tendon rupture manage rehabilitation and return to sports.(40) The questionnaire consists of 17 items concerning pain and kinesiophobia and has 4 answers from “Strongly disagree” to “Strongly agree”. Measured at baseline, 9, 13 and 52 weeks.

Question: Were you afraid to do the prescribed load when performing the exercises? If yes why?  
Measured at 9 weeks

**Compliance with the intervention:** The participants will register the number of exercise sessions they perform each day in a training journal. The timeframe will be from the day they start the exercises to the end of week 9.

**Safety and Adverse events.** The number of serious and minor adverse events is registered in a pre-defined list based on Common Terminology Criteria for Adverse Events(43) and the participants will be asked open questions at each session. Serious adverse events are re-rupture, non-union of the tendon or symptomatic deep vein thrombosis (DVT). Muscle soreness or mild pain is considered inevitable and normal when initiating exercises after a period of immobilization.

**Cost-effectiveness outcomes.** To evaluate the cost-effectiveness of the intervention, we will use self-reported health state as measured by the EQ-5D-5L.(44) Work productivity outcomes are measured using the Work Productivity and Activity Impairment Questionnaire WPAI:GH and condition-related expenses as measured by a self-developed questionnaire. The EQ-5D provides a simple descriptive profile and a single index value for health status and has been used extensively in research to measure QALYs gained and thereby perform health economic evaluations. The questionnaires will be filled out during all follow-ups.

### 13. Participant timeline

Baseline data will be collected at the first appointment in the outpatient clinic. During the intervention the participants will be followed closely and monitored on progression of tendon healing and adverse events. Assessment of outcome takes place at 9, 13, 26 and 52 weeks and will include patient reported questionnaires and physical measurements.

RCT	STUDY PERIOD							
	Enrolment	Post-allocation				Follow-up	Close-out	
TIMEPOINT	Day 1-7	1 week	2 weeks	4-8 weeks	9 weeks	13 weeks	26 weeks	52 weeks
ENROLMENT:								
Eligibility screen	X							
Informed consent	X							
Allocation	X							
INTERVENTIONS:								
Intervention A			←	→				
Intervention B		←	→					
Concurrent observational cohort			←	→				

BASELINE ASSESSMENTS:							
	Pre-score ATRS, IPAQ	X					
	Demographics	X					
ASSESSMENTS questionnaires:							
	ATRS				X	X	X
	IPAQ				X	X	X
	EQ5D-5L	X		X	X	X	X
	Tampa scale of Kinesiophobia TSK	X			X		X
	General health V2.0 (WPAI:GH)			X	X	X	X
ASSESSMENTS physical:							
	ATRA			X	X		X
	Achilles tendon length (by ultrasound)			X	X		X
	Achilles tendon cross-sectional area (by ultrasound)			X	X		X
	Ability to perform single Heel-rise				X		X
	Isometric muscle strength			X	X		X
	Ability to do single leg heelrise				X		
	Muscle endurance				X		X
	Compliance with the intervention			X			
	Complications		←				→

## 14. Sample size

Sample size calculations are based on the primary endpoint ATRS with a clinically relevant difference at 10 point and estimated standard deviation 15 point. With a two-sided 5% significance level and a power of 80%, the sample size will be 37 in each group and a total of 82 participants when allowing for potential dropouts.

## Methods: Assignment of Interventions (for controlled trials)

### Allocation

#### 16a Sequence generation

Randomization of participants is performed using a random number generator on [www.sealedenvelope.com](http://www.sealedenvelope.com) and it will be stratified by sex, as female sex is less present and is associated with lower outcome in the ATRS. Block randomized in random concealed block sizes of 2-4 (1:1) into two parallel groups is used to avoid imbalance in the randomization between the intervention groups.

#### 16b Allocation concealment mechanism

A researcher not involved in the trial will generate the allocation sequence and is the only person who knows the block sizes. The randomization results are kept in opaque sealed envelopes and stored in a locked cabinet where only the project personnel performing the randomization has access.

#### 16c. Implementation

In practice, after a participant has been enrolled, has filled out baseline questionnaires and received initial information regarding the practicalities of participation, the Primary investigator will inform the project secretary of the new participant. The project secretary will open the envelope and assign the participant to the allocated treatment based on randomization. The notes in the envelopes state group allocation number and the intervention. The secretary will inform the participant and the physiotherapy department regarding the randomization results. The randomization is coded so that the Primary investigator does not know which intervention is linked to which group number (Group 1 or 2).

